3.10.2.3 Training of Intervention Facilitators

A two days training will be conducted by the main researcher. Seven to eight staff who are identified by the Senior District Officer will be involved as questionnaire and worksheet interviewers and verbal translators for this study. Dental officers, dental therapists and dental assistants will be the staff of choice to be the facilitators in this study. They are required to be conversant in Bajau language; especially to support the older section of the participants who are more familiar in their local dialect.

The task of the staff is to explain the questionnaire and worksheets items and to be able to assist participants to complete them as accurately as possible. During the talk sessions, the staffs will act as verbal translators and also assist in the question and answer sessions. The delivery of cessation intervention will mainly be in Malay language delivered by the main researcher. The staff will also assist to collect and verify the responses given by participants in the homework logs such as trigger monitoring logs, trigger management, the non chewing game plan worksheets, social support and thought management worksheets.

During the training, the staff will be introduced to the intervention program; the aims and objectives to achieve, the number and brief explanation about the support sessions and the other method of evaluation at the end of the program. A simulation session will be planned to practically expose the staff to the order and details of this intervention. Staff who are not involved in this study will be recruited to act as a BQ chewers to train the staff who are selected to be the facilitators. The names of all the facilitators will be presented and registered under the National Medical Research Registry (NMRR), Ministry of Health (MOH), Malaysia.

Through the simulation, the main researcher could gain some insight on the possible shortcomings or issues that may arise during implementation. Appropriate remedial action and modification can done before intervention commences. A training manual will be prepared for each staff.

3.10.3 Phase 3 Implementation of the study (Field Work)

3.10.3.1 Initiatives to promote study

Prior to the start of the intervention, a **promotional initiative** will be conducted with the village head 3 weeks before the implementation of the study. The purpose of this promotion is to provide knowledge and convince the village head regarding the ill effects of the chewing habit. By agreeing and cooperating to this intervention, his villagers will receive the very first kind of such an intervention in Malaysia to curb the villager's 'addiction'. With adequate knowledge and a right attitude, the village head can have a positive predisposition to encourage his villagers to participate in this beneficial program. Once the trust of the 'strongman (the village head) has been gained', it will be easier to conduct the multi-component intervention in those villages.

Attractive posters and flyers will be distributed to the village head to paste in the allowed public places and for door-to-door flyer dissemination to ensure the villagers are aware of the intervention on the said date. The intervention will be carried on a weekend to obtain maximum participation.

One week before the implementation of the study, villages will be reminded of the program date and villagers who practises BQ habits will be advised to attend the intervention together with family members, relatives or neighbours who also has the similar habit. Moss J et al. (2015) claimed intervening the surrounding community with the similar risk habits can ensure the long term sustainability of habit cessation among chewers.

The first day of the program will be the screening day.

[figure not shown]
[figure not shown]

Figure 3.5 Summary of Promotional Initiatives

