3.3 Sample Population

The Bajau adults are considered as a high-risk individuals alongside Indians, Orang Asli and other indigenous communities in Sarawak and Sabah (OHD, 2018). A high-risk population is defined as communities that practices risk habits such as smoking, drinking alcohol and chewing BQ or living in a community which favours the tendency to take up those habits (OHD, 2002).

Table 3.3 shows that Bajau was the most dominant ethnic group that practiced BQ chewing habit in Kota Belud for the past two consecutive years compared to other races. Data was retrieved from Kota Belud’s District Dental Office oral cancer screening report.

Table 3.3 Local District Screening Report of Ethnic Distribution of BQ Chewers in Kota Belud for 2021-2022

Ethnic	2021	2022
Bajau	307	226
Dusun	300	163
Bumiputera Sabah Lain	97	71

Tentatively, a total of 6 villages will be selected for the conduct of this study; 1 village for pre-test, 1 village for pilot test and another 4 villages for the implementation of the study (2 villages for intervention study and 2 villages for the control arm).

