3.5 Sampling and randomisation method

Prior to randomisation, matching of eligible Bajau villages will be carried out to increase precision and to minimise imbalance across intervention and control groups. This study involves 2 levels of randomisation. The randomisation sequence will be carried out by statistician employed at Faculty of Dentistry, Universiti Malaya.

At the first level of randomisation, all eligible Bajau villages from the total 39 Bajau villages will be paired according to location and average number of BQ chewers in the village (Figure 3.2).

At the second level of randomisation, computer generated random numbers will be used to randomly allocate the Bajau villages in each matched-pair to intervention and control groups. The match-pairs will be randomly selected until the sample size is met.

Bajau villages matched according to average number of BQ chewers in the village

Figure 3.2 Diagram depicting Flow of Matching of Clusters in the Study

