3.6 Allocation concealment

In this study, allocation concealment will be done at cluster level. A senior dental officer (SDO) in Kota Belud Dental District Office who is not involved in cluster identification and recruitment will keep the allocation sequence in a brown envelope in his or her SDO's office until the matched pair are ready to be recruited into the study.

The allocation sequence will be generated by a statistician employed at the Faculty of Dentistry, Universiti Malaya using computer generated tables. The information will be kept confidential until the intervention are assigned to the villages.

Within the cluster, a universal sampling technique will be used to recruit participants into the study. Universal sampling is also known as a total population sampling; which is a type of purposive sampling that involves examining the entire population that have a particular set of characteristics (Laerd Statistics, 2012). All eligible participants who fulfilled the inclusion and exclusion criteria through the screening session will be recruited as study sample. Thereafter, informed consent will be obtained from the participants.

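### The protocol does not require village agreement before the allocation is released, and its approach to village heads presupposes the active programme

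*Protocol*

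**What the plan says.** **Number of villages.** Protocol Section 3.3 tentatively sets "2 villages for intervention study and 2 villages for the control arm".

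**Pairing and allocation.** Under Section 3.5, "all eligible Bajau villages from the total 39 Bajau villages will be paired according to location and average number of BQ chewers". Random numbers then "randomly allocate the Bajau villages in each matched-pair to intervention and control groups". More pairs can be added: "The match-pairs will be randomly selected until the sample size is met".

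**Release of the allocation.** Section 3.6 keeps the sequence in an envelope at the district dental office "until the matched pair are ready to be recruited into the study". It adds: "The information will be kept confidential until the intervention are assigned to the villages". It does not say what makes a pair ready.

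**Approach to the village head.** Section 3.10.3.1 describes one approach, in Phase 3, three weeks before implementation. The message is "By agreeing and cooperating to this intervention, his villagers will receive the very first kind of such an intervention in Malaysia". Once the head's trust is won, "it will be easier to conduct the multi-component intervention in those villages".

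**Timetable.** Section 3.25 has a row for selecting and recruiting villages in May 2023 (week 1), placed under Phase 2, which mentions a meeting with the pre-test village head. A second head meeting, for the pilot, is in May (week 4). Promotion is in July (week 1). No meeting is listed by name for the heads of the trial villages.

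**Refusal.** No section says what happens if a village declines. The replacement rule in Section 3.9 covers individual participants only.

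**The concern.** The village is the unit of randomisation, so a village's decision to take part should not depend on its arm. If a head is asked after allocation, or asked in terms that reveal the arm, the villages that stay in can differ between arms, for instance with keener heads in one of them. Section 3.10.3.1 relies on the head to encourage villagers to join, so his attitude could influence who enrols and possibly who quits. Randomisation no longer protects against such a difference, and analysis cannot repair it.

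Two pairs leave little room to absorb this. A refusal also leaves the partner village without its match, and the rule for drawing pairs does not say whether a pair may be replaced after its allocation is known. This point concerns agreement by the village. It is separate from individual consent.

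**Working it through.** No figure in the protocol decides the point, so the main check sets the sections side by side.

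**1. Counts.** Four study villages in matched pairs give 4 / 2 = 2 pairs. The pool of 39 villages gives at most 19 pairs, before the pre-test village, the pilot village and any ineligible villages are removed. Replacement pairs could therefore be found.

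**2. Order of steps as written.**
- Section 3.5: pair, then allocate within pairs. No agreement step.
- Section 3.6: open the envelope when the pair is ready for recruitment. On a plain reading, recruitment follows release. Readiness could instead mean that both villages have already agreed.
- Section 3.10.3.1: ask the head to agree, three weeks before implementation.
- Section 3.25: this approach falls in July. The May row could include earlier recruitment of the trial villages, but it sits under Phase 2 and names only the pre-test head.

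**3. Each reading taken to its end.**
- *Envelope first, head second.* The head is asked about an arm already fixed. His answer can depend on it.
- *Head first, envelope second, using the Section 3.10.3.1 message.* Heads of villages later allocated to control will have agreed to a multi-component programme that Sections 3.1 and 3.10.3.2 do not give them. They may withdraw when they learn this, which is again after allocation.
- *The Section 3.10.3.1 message used in intervention villages only.* The arm is then known when it is delivered, and no approach to control heads is described.

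Each reading leaves a route by which a village's participation depends on its arm.

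**4. What the draw rule does.** Drawing pairs until the sample size is met restores numbers after a refusal. If the refusal was made with the arm known, the redraw keeps only pairs whose members accepted their arms. That is selection by arm.

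**5. Size if a pair were lost and not replaced.** The plan's figure reproduces first. With 38.64% against 9.09%, two-sided 0.05, 80% power and Fleiss continuity correction, n = 38 per arm, 76 in total; 76 × 1.2 = 91.2, rounded up to 92. With equal village sizes, losing one of two pairs takes 38 per arm to 19. The formula is

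power = Φ{[|p1 − p2| − 1.96·√(2·p̄·q̄/n)] / √[(p1·q1 + p2·q2)/n]}, with p̄ = 0.23865.

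- n = 38: (0.2955 − 0.1917) / 0.0917 = 1.13, power 87%.
- n = 19: (0.2955 − 0.2711) / 0.1297 = 0.19, power 57%.

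These are individual-level values without clustering or continuity correction. One village per arm would remain, so arm and village could not be told apart. This is a conditional illustration, since the draw rule may replace the pair.

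**The case against.** The strongest reply is that the protocol never says the envelope is opened before the head is approached. Holding the sequence until the pair is ready can be read as agreement first and opening second. The May row for village recruitment precedes the July promotion by about two months. Section 3.10.3.1 is written as promotion, not as a defined village-consent step, and the protocol sometimes uses the word intervention for both arms. Figures 3.1 and 3.5 and the flow chart in Section 3.23 could not be read for this point and might show the order.

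Most of this stands. A reader might infer that agreement is first sought after allocation and that heads know their arm. The documents do not support this as fact; they leave the order open. A reader might also infer that one refusal costs a quarter of the participants (92 / 4 = 23 per village), or attach a probability to refusal. The first ignores that a further pair can be drawn, and for the second the documents give no rate.

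The reply does not remove the concern. Readiness is undefined, no section makes village agreement a condition for opening the envelope, and the Section 3.10.3.1 message fits only the active arm. The agreement-first reading still leaves control heads having agreed to something their villages will not receive.

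**Conclusion.** The concern holds as a gap in the order of steps, together with a message that does not fit both arms. The protocol does not require village agreement before the allocation is released. Its only described approach to study-village heads either implies the arm is known or misdescribes the control arm. It has no rule for a village that declines. The result could be selection of villages by arm, at the level where randomisation is meant to prevent it.

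The size of the risk is not quantified, because it depends on a refusal rate that the documents do not give. The case for acting rests on the small number of pairs (itself tentative), on a draw rule that does not bar redrawing after a known allocation, and on the low cost of closing the gap. This should be changed before trial villages are approached. It does not show that the trial's randomisation has failed.

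**What to change.** Revise Sections 3.5, 3.6 and 3.10.3.1 and the timetable in Section 3.25 together, so that they state:

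1. For each randomly drawn pair, both village heads are approached with one neutral explanation that describes both arms.
2. Both heads agree to take part in either arm before the envelope is opened. This defines when the pair is ready.
3. A pair may be replaced only before its envelope is opened.
4. A village that withdraws after opening is reported and kept in its allocated arm.

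The Section 3.10.3.1 message should be reworded so that it does not promise the multi-component programme before allocation. Any figure showing the sequence should be brought into line.

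Cost: head meetings for drawn pairs move earlier, and a few extra heads are met if a pair declines. There is no need to approach all 39 villages.

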3.10.3.2 Implementation of the Study

Control Group

The community screening program for the control group will be organised at the community hall. Villagers who attended the screening program will first be registered and screened for eligibility to participate in the study (**Checkpoint 1**). The eligible participants will be briefed on the nature of the intervention and will be invited to participate. A copy of 'Patient Information Sheet' (PIS) (Appendix A) will be explained and given for reference about the study details and written informed consents (Appendix B) will be obtained from the villagers prior admitting them into the study.

Only consented participants will be interviewed by the trained interviewers (**Checkpoint 2**). Information regarding demographics details and baseline information of BQ chewing behaviours, BQ composition, BQ dependency levels, reasons for chewing, readiness and self-perceived barriers to quit will be obtained. No intra-oral clinical examination will be carried out in this study.

Upon completing of the interview, participants will be given an educational booklet which contains general information regarding AN and BQ, risk associated with BQ chewing behaviour, cessation strategies that are modeled after tobacco cessation and researcher's contact information. After an one-to one explanation about the educational booklet to the participants by the interviewer, they will be ushered to saliva collection counter (**Checkpoint 3**) to provide their baseline saliva sample. Participants will be thanked and given a token of appreciation before they are ushered out of the community hall.

Participants will be provided with an appointment card to return on the 22-day, 1-month and 3-month for follow-up. Follow-up questionnaire and saliva samples will be taken on 22-day and 3-month, whereas a community perception analysis will be performed at 1-

month together with completion of follow-up questionnaire. The summary of participant's flow for the control group is illustrated in Figure 3.6.

[figure not shown]

Figure 3.6 Summary of Participant's Flow for the Control Group in this study

Intervention group

Screening (Day 0)

The community screening program for the intervention group will be organised at the community hall on a Saturday. Villagers who attend the screening program will first be registered and screened for eligibility to participate in the study (**Checkpoint 1**). The eligible participants will be briefed on the nature of the intervention and will be invited to participate. A copy of 'Patient Information Sheet' (PIS) (Appendix A) will be given for the reference about the study details and written informed consents (Appendix B) will be obtained from the villagers prior admitting them into the study.

Only consented participants will be interviewed by the trained interviewers (**Checkpoint 2**). Face-to-face interviews will be carried out to gain participant's information regarding demographics details and baseline information of BQ chewing behaviours, BQ composition, BQ dependency levels, reasons for chewing, readiness and self-perceived barriers to quit habit. No intra-oral clinical examination will be carried out in this study.

Upon completion of the interview, participants will be briefly explained and given an educational booklet which contains general information regarding AN and BQ, risk associated with BQ chewing behaviour, cessation strategies that are modeled after tobacco cessation and researcher's contact information. They will then be ushered to saliva collection counter (**Checkpoint 3**) to provide their baseline saliva sample.

Participants will be thanked and given a token of appreciation before being ushered out of the community hall and will be reminded to return the next day (Sunday) to initiate the first support session for the cessation intervention. For every intervention session attended by the participants, they will be monetarily incentivized for their time and commitment for cessation. Appointment card will be provided to ease participants reference of support session dates.

A self explanatory video presentation regarding general information of AN and BQ, the ill health effects of BQ and introduction and importance of cessation program will be continuously played **for the non- chewers in the village hall** to increase their knowledge and awareness while they are waiting for their family members. who are undergoing the screening. This can help maximise their support for their loved ones who are trying to quit the risk habit.

The subjects will be assigned into a group of seven participants and the appointments for each group participants will be given across the week. A total of 2 group sessions will be made in a day; a morning session and an afternoon session. Participants will be sought of their preferred time to increase participation in the intervention group.

[figure not shown]

Figure 3.7 Flow of Participants on the Screening of the study (Day 0)

1st Session (Day 1)

On the **1st session of the intervention (Day 1)**, attendance of all eligible and consented participants will be taken at **Checkpoint 1** and the nature of intervention will be introduced through a **brief talk**. The information that the participants will undergo 5 sessions of support and information group designed to assist them to quit BQ chewing habit over 22 days period will be emphasized and they will be reminded that their continuous commitment to the intervention is utmost important to their future cessation.

They will also be briefed that each support session will consume approximately 1-2 hours. It will be conducted by the main researcher in Malay language (Bahasa Melayu) and

translated by trained facilitators into Bajau language verbally. A translation script will be prepared before initiation of the intervention for standardization to minimise bias or any poor explanation in Bajau language.

After the brief introduction, an **educational talk** will be delivered to the study participants by the main researcher. The content of the talk will be based on the topics of the educational booklets (general information regarding AN and BQ, risk associated with BQ chewing behaviour through projection of captivating graphical aids, cessation strategies that are modeled after tobacco cessation and researcher's contact information) but in a more detailed and interactive manner. An aid of Microsoft Powerpoint multimedia presentation will be used. A two-way communication mode will try to be sought throughout the entire talk. Participants will be encouraged to participate actively during the educational talk session. The aim of the educational talk is to increase the chewer's awareness, motivation and to enhance their commitment to cease behaviour. Participants too will be encouraged to share their experience and their feelings of chewing BQ and what are the challenges they face while practicing this habit.

Following the talk, participants will be introduced on the **topical worksheets**. For Session 1, 3 topical worksheets will be administered to participants; trigger monitoring logs (Appendix D), trigger management logs (Appendix E) and arecoline fading worksheet (Appendix F). A brief explanation regarding triggers to chew BQ, example on how and different types of strategies available which could be utilised to manage the triggers and the concept of arecoline fading will be discussed with the participants. Three checkpoints will be prepared to assist participants practically and individually on how to fill the worksheet. Before proceeding to the checkpoints, participants will be divided into a group of 7 people and will be assisted by trained facilitators on completion of the worksheets.

Checkpoint 2 will cater for the completion practice of trigger monitoring logs (Appendix D). Explanation regarding what are triggers, different types of triggers and situations that make this triggers arise to promote chewing behaviours will be further discussed individually based on participant's experience. Common examples such as urges to chew after a meal or after meeting a close friend will be explained to participants to aid their comprehension. Participants will be asked to keep a written record of the number of quids chewed in a day, the situation and the mood that they are in prior to the initiation of the chew. The record should be written before the participants start the chew. The daily records of trigger logs of a minimum of 3-4 days will be required for a good analysis.

Checkpoint 3 will cater for the completion practice of trigger management log (Appendix E). This management strategies are self-control strategies that one can abide with to manage their trigger situation. In a single day, participants can experience many and varied types of triggers that lead them to chew. During the intervention, participants will only be encouraged to intervene in two or three triggers in a week. This gradual approach is so that participants can cope with the withdrawal symptoms that results from the small changes. Participants will be guided on how to systematically decide on the strategies. All strategies used and advocated by the participants should be written in the worksheet. It is best that chewers tackle the easiest trigger situations before moving to a more difficult situation. Chewers would be first consulted in this management strategies as they are the best persons who have a good sense of their situations and which that could be intervened.

Checkpoint 4 will cater for the completion practice of arecoline fading concept and worksheet (Appendix F). The rationale of this concept is to gradually reduce the participant's physical dependence on AN. This can be done through the rate reduction

method prior to the quit date. Participants will be advised to reduce 1 quid within 2-3 days or at a reduction rate of 10% BQ consumption in 2-3 days. By applying this concept, participants will be able to reduce the intensity of their withdrawal symptoms on the quit day and make their quitting experience less difficult. This fading concept can be a substitute for pharmacological approaches and can be eliminated for participants who would like to quit in a cold turkey manner on the quit date.

From **Checkpoint 2-4**, participants will be required to fill their triggers and strategies that they personally could make to manage their triggers. Participants will be given a firsthand experience on it by the facilitators guiding the participants to remember the previous day’s triggers and ways they could manage those triggers. With personalised examples and guidance, they will be more self-efficient to complete worksheets in the following days. Participants will be required to fill those worksheets for a minimum of 3-4 days. The **worksheets will be collected by facilitators on Day 5 (Friday)** of the following week. The main researcher will review the trigger logs and trigger management logs to provide a summary on Session 2.

[figure not shown]

Figure 3.8 Summary of Participant’s Flow on the 1st Session of the Intervention (Day 1)

2nd Session (Day 8)

On the **2nd session of the intervention (Day 8)**, after participants are registered at Checkpoint 1, **a summary talk of the triggers within that community (village) and potential strategies to manage** triggers given by the participants will be projected and further discussed. Participants will be briefed that quitting chewing is more than cutting down the betel quid numbers or antagonising the triggers. A lifestyle change is very pertinent in making an ex-chewer remain abstinent. Strategies such as lifestyle changes, excuses to reject chew invites and usage of fake chew objects will be taught to participants to empower them to manage their triggers.

Checkpoint 2 will be prepared for completion practice of Lifestyle Change : Non-chewing Game Plan Worksheet (Appendix I). There are 6 questions in this worksheet regarding the lifestyle changes that the participants can answer to assist them to quit the habit; namely “What will you do to make betel quid unavailable to you”, “What will you do to increase time spent in non-chewing areas or to increase doing non-chewing activities”, “How can you get help from others while trying to quit”, “What will you do to manage stress successfully”, “What will you do from keeping from gaining weight” and “What will you do to be physically active (if it is relevant)”. All these 6 questions will be explained further to participants by the facilitators followed by discussion with the participants.

Checkpoint 3 will be prepared for completion practice of Coping with High Risk Situation : Non-chewing Game Plan Worksheet (Appendix J). For each specific high-risk situation identified, participants will be asked to describe the event, persons that they might be with, what were they doing, thinking, or feeling at the time. Participant will be asked to develop a full set of coping strategies to deal with the situation without chewing. They will

be reminded that these high risk situations are temporary. They can utilise the 3As (Avoid, Alter, use Alternatives) of coping mechanism skills (Appendix H) and relaxation exercises (Appendix G). The participants will be reminded that this is a crucial planning for them to remain abstinent.

Checkpoint 4 will be prepared to teach participants on the **brief relaxation strategies** (Appendix G). Meditative and deep-breathing technique are taught to participants. Participants will be reminded that daily use of this relaxation procedure can help reduce chewer's overall stress level; which in return may help participants to quit chewing more easily. The participants can utilise this strategy to avoid the urges to chew and to manage their triggers. These strategies will take around 10-20 minutes and can be performed while sitting on a chair.

Checkpoint 5 will be prepared to teach participants on the **brief coping skills** (Appendix H). Without being equipped with skills to cope for stressful environment, it will be impossible of any chewer to be a permanent non-chewer. Bandura (1997) stated successful coping with high risk situation leads to increase sense of self-efficacy and determines an individual's probability of maintaining chewing abstinence. Three main coping skills will be taught to participants (3As); avoiding the trigger, altering the trigger situation and finding an alternative when the chewing trigger arise.

All checkpoints will serve to practically guide participants on their checkpoint topics. At the end of Session 2, participants will be reminded of the quit day that will be on Day 15 (the morning of the third session) and concept of arecoline fading too will be re-emphasized.

[figure not shown]

Figure 3.9 Summary of Participants' Flow on the 2nd Session of the Intervention (Day 8)

3rd Session (Day 15)

On the **3rd session of the intervention (Day 15)**, it will be the quit date for the participants. Participants will be registered at **Checkpoint 1**. Main researcher and facilitators will discuss with the participants about the potential withdrawal symptoms that they may experience. Participants will be made aware that withdrawal symptoms will only persist at most up to 2 weeks, and after that period, the symptoms will fade away and not cause any difficulty. Coping strategies to combat the withdrawal symptoms will be discussed with the participants to help prevent any relapse (**Checkpoint 2**). The main researcher and facilitators will remain supportive to the participants and not to act in a judgmental manner regardless of the individual's chewing status. Physical activities that are suitable for elderly and within the vicinity of the community will be recommended for participants to cope with the withdrawal symptoms.

Checkpoint 3 will be prepared for completion practice of Social Support for Non-BQ Chewing Worksheet (Appendix K). It is a tool to maximise the social support of the participant to quit the behaviour. Social support can be a good source of motivation and may also act as a buffer for stressful situations. Thus, they play a positive role in the success of participants in remaining abstinent. Thus, in this checkpoint, the participants will be guided to identify their social support and record behaviours of others that are helpful and not helpful in their non-chewing efforts, and also activities that the participants would like others to increase or decrease to help them in their journey of quitting chewing. Facilitators will personally guide the participants to complete this worksheet to give them a headstart.

[figure not shown]

Figure 3.10 Summary of Participants' Flow on the 3rd Session of the Intervention (Day 15)

4th Session (Day 18)

On the **4th session of the intervention (Day 18)**, participants will be registered at Checkpoint 1. Discussion on the overall quitting experience of the participants will be held in the hall on how participants coped with triggers, the challenges in the high risk situations and the benefits they gained from the 3 days of quitting experience will be highlighted during the discussion. The arecoline fading worksheet will be collected and reviewed and discussed with participants. The facilitators will further emphasize the negative health effects of BQ chewing and accentuate the oral cancer risk that is contributed by BQ chewing behaviour. Additional coping strategies will be discussed to address newer urges to chew. Reinforcement will be given for both quitters and current chewers through a talk by the main researcher.

[figure not shown]

Figure 3.11 Summary of Participants' Flow on the 4th Session of the Intervention (Day 18)

5th Session (Day 22)

On the **5th session of the intervention (Day 22)**, participants will register their attendance at **Checkpoint 1** and will be required to complete a follow-up questionnaire. The questionnaire will enquire regarding brief personal particulars, patient's compliance, current chewing status, number of cut-down of habit by the participants (quid/day), total number of sessions attended and reasons if absent and the BQ composition if participants are still chewing.

Later, a discussion on the overall quitting experience will ensue. Participants who have relapsed and started chewing but are willing to attempt to quit again will be encouraged. **Strategies for managing thoughts** that could lead to relapse will be introduced. The participant's lifestyle changes that supports quitting will be reviewed. Usage of "excuses" for not chewing and employing "fake chew" will be reinforced.

The **Positive and Negative Thoughts Worksheet (Appendix L)** will be a strategy to manage the thoughts that participants might have through their quitting journey. This method is based on the notion that mood is related to the balance of the positive and negative thoughts. When negative thoughts outweighed the positive thoughts, the result is a depressive, anxious, angry or other symptoms that precipitate the behaviour of risk habit such as chewing to overcome it (Brown RA et al. 2003). The thoughts with a clear message of positivity or negativity should be recorded and it is curcial to discern which type of thoughts dominates in this process. The negative thoughts can be managed with the coping skills that they were thought before. The main researcher will brief all participants regarding this thought management through a talk.

Checkpoint 2 will be prepared for completion practice for Positive and Negative Thoughts worksheet (Appendix L). One of their current positive and negative thoughts will be used as a practice. At the end of session 5, **Checkpoint 3** will be prepared as saliva collection counter for participants to provide their 22-day saliva samples.

[figure not shown]

Figure 3.12 Summary of Participants' Flow on the 5th Session of the Intervention (Day 22)

3-month follow up (Day 90)

On **3- Month follow up**, participants will be assessed of their chewing abstinence through a follow up questionnaire after registration (**Checkpoint 1**). The items that will be required are brief personal particulars, participant's current chewing status, number of cut-down of habit by the participants (quid/day) and BQ composition if participants are still chewing. All participants will be motivated and encouraged regardless their success in quitting the BQ behaviour. A repeated educational talk of adverse effects of AN and BQ chewing habit will be given. A summary of community perception will be informed to the participants and they will be encouraged to contact research team if they needed any form of help in cessation in the future.

Checkpoint 2 will be prepared as a saliva collection counter for participants to provide their 3-month saliva samples. Participation on each session of the intervention and follow-up will be monetarily incentivized to maximise the participation rate.

[figure not shown]

Table 3.13 Summary of Participants' Flow on the 3-Month Follow up of the Intervention (Day 90)

Table 3.4 Descriptive Summary of Intervention Arm Activities

Session	Day	Description of Session	By: Brown (2003), Moss et al (2015)	Document Reference
1	1	
Introduction of program, ground rules, informed consent
 
 • Health effects of AN and BQ chewing, esp. oral cancer risk • Discussion on self - monitoring for triggers (logs introduced) • Discussion on trigger management log (logs introduced) • Discussion on concept of arecoline fading and rate reduction prior to quitting (log introduced) 		
Appendix D
 
Appendix E
 
Appendix F

2	8	
Review trigger logs, discuss self - management approach
 
 • Discussion on lifestyle change to support quitting (logs introduced) • Discussion on "excuses" for not chewing, usage of "fake chew" • Explanation about brief relaxation exercise and coping skills • Reminder to participants about arecoline fading and that Quit Day is morning of the next session 		
Appendix I & J
 
Appendix G & H

3	15	
QUIT DAY. Facilitator is tasked with reminding participants to be supportive and non-judgmental, regardless of individual chewing status
 
 • Remind participants that withdrawal symptoms, if applicable, are generally worse in first 2 weeks, but will pass • Discuss coping strategies to prevent relapse • Plan to maximize social support for non – chewing (eg. talk) (log introduced) • Recommend physical activity (if applicable) 		
Appendix K

4	18	
Overall discussion of quitting experiences, including coping with triggers and high - risk situations, short - term benefits from quitting chewing
 
 • Discussion on negative health effects of AN/BQ chewing again, including oral cancer risk (reinforcing this throughout derived from pilot testing) • Discuss additional strategies for coping with urges to chew 		
5	22	
Continue overall discussion of quitting experience
 
 • Encourage participants who have relapsed to attempt to quit again • Introduce strategies for managing thoughts that can lead to relapse • Review lifestyle changes that support quitting • Reinforce usage of "excuses" for not chewing, employing "fake chew" • Final remarks about planning for the future 		
Follow -up Questionnaire
 
Appendix L

